7.1.1 Screening

At screening, the patient's eligibility will be defined.

7.1.2 Visit 1 (same day as Screening)

- Collection of demographic and disease-related data (age, gender, diagnosis, age at onset of symptoms, age at diagnosis, severity and location of myotonia and severity and location of muscle stiffness, for both using numeric rating scale (NRS)).
- Performing a 6-Minute-Walk-Test (meters).
- Clinical evaluation of muscle strength of the following muscles, using the MRC-Scale (0-5): on both sides thenar and hypothenar, m. biceps brachii, m. triceps brachii, m. deltoideus, m. quadriceps femoris, m. tibialis anterior and gastrocnemius muscles.
- Semiquantitative measurement of cutis and subcutis, subcutaneous fat and muscle thickness by muscle ultrasound of the following muscles: on both sides thenar and hypothenar, m. biceps brachii, m. triceps brachii, m. deltoideus, m. quadriceps femoris, m. tibialis anterior and gastrocnemius muscles. Measurements will contain the thickness of cutis in millimeters, the thickness of subcutaneous fat in millimeters, the muscle thickness in millimeters at the point of measurement of the MyotonPro® and a semiquantitative measurement of muscle echogenicity, using the Heckmatt scale I-IV.
- Measurement of relaxation time, stiffness and elasticity of the following muscles, using the MyotonPro® device: on both sides thenar and hypothenar, m. biceps brachii, m. triceps brachii, m. deltoideus, m. quadriceps femoris, m. tibialis anterior and gastrocnemius muscles. For the documentation of the results, please see section "MyotonPro® device".

7.1.3 Visit 2 (+1-7 days after day 1)

- Measurement of relaxation time, stiffness and elasticity of the following muscles, using the MyotonPro® device: on both sides thenar and hypothenar, m. biceps brachii, m. triceps brachii, m. deltoideus, m. quadriceps femoris, m. tibialis anterior and gastrocnemius muscles. For the documentation of the results, please see section "MyotonPro® device".

The total duration of assessments performed on screening and visit 1 will be approximately 2 hours. The total duration of visit 2 will be about 30 minutes.

The data collected will be stored in a local database, that is password protected and only read- and editable for persons directly involved in the study.

7.1.4 MyotonPro® Device

The MyotonPro® Device is a commercially available electronic device for non-invasive measurement of muscle stiffness, muscle tone, relaxation periods and viscoelasticity. The method of measurement consists of recording damped natural oscillation of soft biological tissue in the form of an acceleration signal and the subsequent

simultaneous computation of the parameters of State of Tension, Biomechanical and Viscoelastic properties. A damped natural oscillation is induced by an exterior, low force quick-release mechanical impulse under constant pre-load. The tip of the myometer will be placed on the tissue perpendicular to the underlying muscle. The device gets activated by a slight pressure on the tip which exerts a local impact on the tissue utilizing a brief mechanical impulse. This causes a minor deformation of the underlying muscle tissue. After the impact, the tip is quickly released, and the damped oscillatory behaviour of the tissue will be recorded by an accelerometer in the device. The viscoelastic stiffness of the underlying tissue will automatically be calculated using the following equations (S=stiffness; D=elasticity; R=relaxation):

$$S = \frac{a_{max} \cdot m_{probe}}{\Delta l} \quad D = \ln \left(\frac{a_1}{a_3} \right) \quad R = t_R - t_1$$

S stands for stiffness, measured in N/m, and is the biomechanical property of a muscle that characterizes the resistance to a contraction or to an external force that deforms its initial shape. Elasticity **D** is the logarithmic decrement of a tissue's natural oscillation. Elasticity is the biomechanical property of a muscle that characterizes the ability to recover its initial shape after a contraction or removal of an external force of deformation. The Relaxation **R** is the time for a muscle to recover its shape from deformation. The functionality of the MyotonPro®, its way of measurement and the calculations have been tested and validated in a high number of clinical studies. Therefore, this study is not intended to validate the measurements of the MyotonPro® device itself nor its safety and accuracy of measurements, but to evaluate measurement results in patients with neuromuscular diseases and elaborate reference values.

7.1.5. Six-Minute walk test

The six-minute walk test (6MWT) measures the distance an individual is able to walk over a total of six minutes on a hard, flat surface. The goal is for the individual to walk as far as possible in six minutes. The individual is allowed to self-pace and rest as needed as they traverse back and forth along a marked walkway. The 6MWT has been used with a variety of other conditions than the chronic obstructive pulmonary disease (COPD) such as heart failure and stroke and is widely used in neuromuscular diseases [26]. The six-minute-walk-test will be conducted as recommended by the American Thoracic Society [27]. In this study, the six-minute-walk test will be performed once on visit 1 to detect the impact of muscle weakness, muscle stiffness and myotonia on muscular endurance.

7.1.6. Semiquantitative muscle ultrasound

Muscle ultrasound is an ideal imaging modality that allows for atraumatic, noninvasive, radiation-free point-of-care neuromuscular imaging [28]. Muscular dystrophies are typically associated with an increase in the echogenicity from the muscle substance, distal attenuation of muscle echo and a corresponding loss of bone echo. Spinal muscular atrophies and neuropathies also showed an increase in muscle echo along with atrophy of the muscle and increase in depth of subcutaneous tissue, but a persisting bone echo. In several other myopathies, similar changes are seen [29]. In semi-quantitative muscle ultrasound, muscle intensity will be documented using the 4-point Heckmatt score [28].

7.1.7. Hand-held Dynamometry of muscle strength

Muscle strength will be assessed by handheld dynamometry using the MicroFET2 myometer, produced by Hoggan Health Industries. This test is widely used in patients with neuromuscular diseases [30, 31]. To perform a test, the examiner holds the dynamometer stationary while the patient exerts a maximal force against the dynamometer. The patient makes a gradual increase in force and then completes an isometric hold for 4-5 seconds. The following muscle groups will be tested: Arm abduction, elbow flexion, elbow extension, knee extension, knee flexion, foot extension, foot flexion.

7.2 Completion of a Patient's Participation in the Study

7.2.1 Completion of a Patient's Participation in the Study

The length of a patient's participation will be from the time the informed consent form is signed until the last planned assessment/visit. A patient will be considered "completed" if all study procedures of the second visit have been carried out.

7.2.2 Premature Patient Discontinuation from the Study

Patients are free to withdraw consent and/or discontinue participation in the study at any time, without prejudice to further treatment. For patients who prematurely discontinue from the study, the Investigator or designee will contact the patient 4 to 7 days after withdrawal to assess any AEs. Post-study serious adverse events (SAEs) will be reported accordingly. A patient's participation in the study may also be discontinued at any time at the discretion of the Investigator. Patients who are prematurely withdrawn from the study will be asked to complete all discontinuation assessments prior to withdrawal, if possible. A patient will be considered early terminated if the patient does not complete the study after enrollment. Patients who are withdrawn from the study will not be replaced (i.e., a patient's study number will not be reused); however, additional patients may be enrolled to offset patient dropouts.

7.3 Discussion of Study Design, Including Choice of Control Group

This is a monocentric, blinded, cross-sectional explorative study designed to evaluate myotonia, muscle stiffness and elasticity in 70 patients with neuromuscular disorders. For statistical comparison, we plan to recruit 20 healthy subjects as a control group.

8 RISKS AND BENEFITS

8.1 Summary of Potential Risks

Study-specific procedures and associated risks are bulleted below:

- Functional testing (six-minute-walk-test): falls, shortness of breath, muscle soreness, myalgia and fatigue

8.2 Summary of Potential Benefits

Analyzing muscle stiffness and myotonia in an easy and non-invasive way could help to detect dystrophic

and non-dystrophic myotonia earlier on the course of the disease and support early diagnosis. Besides, treatment effects could be objectively measured and observed.

9 ADVERSE EVENTS REPORTING

Detailed listings of patients who experience AEs or SAEs will be presented. The incidence of treatment-emergent AEs and SAEs will be tabulated (frequencies and percentages) by severity, and by relationship to treatment. Adverse event severity will be categorized as mild, moderate, or severe. In tabulating severity of AEs on a per-patient basis, the greatest severity will be assigned to a patient should there be more than one occurrence of the same AE with different reported severities. Relationships of the AE to treatment will be categorized as not related, unlikely related, possibly related, or related. The highest level of the association will be reported in patients with differing relationships for the same AE. Listings of AEs and SAEs for all patients will be provided, which will include severity and relationship to the study procedures, the actions taken regarding the study procedures as well as the patient's outcome. A separate listing for patients who withdraw from the study due to AEs will be provided. The incidence of AEs leading to study discontinuations will also be summarized.

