7 INVESTIGATIONAL PLAN

7.1 Study Design

This is a cross-sectional, blinded, monocentric, explorative study to evaluate the stiffness, muscle tone, relaxation periods and elasticity of various muscles in patients with neuromuscular diseases. Local ethic's approval is obligatory before the recruitment of the first patient. The patient must provide informed consent prior to performing any protocol-related procedure at the screening visit. The estimated duration of this study is 12 months or as soon as a total of 50 patients with neuromuscular diseases and 20 healthy volunteers are evaluated. The person assessing the muscle stiffness and myotonia, using the MyotonPro® device, will be blinded to the diagnosis, to medical history as well as results from the clinical tests (clinical muscle strength, 6-minute-walk-test) and results of muscle ultrasound assessments. The study duration for one patient or one healthy volunteer is two to a maximum of seven days. All relevant data will be assessed within visit 1. At the second visit (visit 2), only measurements of the MyotonPro® will be repeated to evaluate the reliability of the measurements.

Both patients and healthy volunteers will perform the following assessments:

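### Section 9 tabulates adverse events by relation to a treatment the study does not give, and the only event enquiry described is for participants who withdraw

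*Protocol*

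**What the plan says.** Section 9 sets the rule for the tables: "The incidence of treatment-emergent AEs and SAEs will be tabulated (frequencies and percentages) by severity, and by relationship to treatment". It then fixes the causality scale on the same basis: "Relationships of the AE to treatment will be categorized as not related, unlikely related, possibly related, or related". For the listings it changes basis. "Listings of AEs and SAEs for all patients will be provided", and their content is described as that "which will include severity and relationship to the study procedures", together with any action taken on those procedures.

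The design statement in section 7.1 reads "This is a cross-sectional, blinded, monocentric, explorative study". Sections 7.1.1 to 7.1.3 list eligibility, demographic and disease data, the six-minute walk test, MRC strength grading, muscle ultrasound and the MyotonPro measurement. No study treatment appears.

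On finding out about events, section 7.2.2 says that for those who discontinue early the investigator or a designee "will contact the patient 4 to 7 days after withdrawal to assess any AEs". Section 7.1 places all relevant data collection in Visit 1 and says of Visit 2 that only the device measurements "will be repeated to evaluate the reliability of the measurements". Section 8.1 names the risks of the walk test: "falls, shortness of breath, muscle soreness, myalgia and fatigue".

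**The concern.** Two separate things need attention.

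The first is an inconsistency on the page. An event is treatment-emergent when it begins or worsens after treatment starts, and relatedness to treatment presupposes that a treatment was given. Here there is neither. Whoever programs the tables must either leave them empty or silently replace the rule with another one. The listings use a workable basis, so a fall during the walk test could be listed as related to a study procedure and still have no place in the table meant to summarise it.

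The second is a gap in how events come to be known. The reporting in section 9 covers everyone, but the one enquiry described reaches only those who leave early. Some of the walk-test risks can surface after the participant has gone home. If completers are not asked, such events depend on spontaneous report, and the tabulated incidence would not mean the same thing in completers as in withdrawals.

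**Working it through.** The protocol states no adverse-event rate, withdrawal rate or expected count, so there is no figure to reproduce. The check is a comparison of sections.

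**Attribution basis**

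| Output in section 9 | Which events | Related to what |
|---|---|---|
| Incidence tables | treatment-emergent | treatment |
| Causality scale (four levels) | – | treatment |
| All-patient listings | all AEs and SAEs | study procedures |

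1. Is there a treatment that the first two rows could refer to? Sections 7.1.1 to 7.1.3 contain assessments only.
2. Could it be the patients' routine care? The study does not give or assign that care, the Visit 1 data list in section 7.1.2 does not record when it started, and the healthy volunteers have no neuromuscular treatment to relate an event to.
3. The first two rows therefore have no referent and conflict with the third. Taken literally, no event qualifies for the incidence table, whatever happens to participants. The listings are unaffected.

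**How events are found**

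| Participant | Contact described | Enquiry about events stated? |
|---|---|---|
| Everyone, Visit 1 (7.1.2) | day 1, walk test performed | no |
| Completer, Visit 2 (7.1.3) | 1 to 7 days after day 1, device only | no |
| Early withdrawal (7.2.2) | 4 to 7 days after withdrawal | yes |

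4. Section 7.2.1 counts a participant as completed once the Visit 2 procedures are done. It adds no later contact.
5. Of the five risks in section 8.1, falls and shortness of breath would mostly occur during the walk test, in front of staff. Muscle soreness, myalgia and fatigue can develop later. The exposed part is thus delayed events in completers.

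**Can the shortfall be sized?**

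Let *p* be the share of completers who have a delayed event and *c* the share of those events that are recorded without a planned question.

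- Recorded incidence of delayed events in completers = *c* × *p*.
- Shortfall = (1 − *c*) × *p*.

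Neither *p* nor *c* is in the protocol. Over the full range of *c*, the shortfall runs from 0 (*c* = 1, all volunteered or asked for in practice) to *p* (*c* = 0, none recorded). Nothing in the documents narrows that range.

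**The case against.** The strongest reply is that the treatment wording is a template remnant. Section 9 itself speaks of study procedures, so the intended meaning can be recovered. That is fair as to intent and is why the point is minor, but the section still gives two rules and the tables follow the unusable one. Leaving table details to a separate analysis plan does not help either, because the protocol has already fixed the basis.

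On the enquiry, a reader might infer that only withdrawn participants are asked about events. The documents do not say so. The visit lists are silent, and silence is not a rule. Section 9 promises listings for all patients and a separate one for those who withdraw because of an event, which presupposes data from people who stay. The sentence in section 7.1 can be read as naming which Visit 1 assessments are repeated, without barring staff from noting events. The paper case report form, which is not shown, may carry a question. All of this stands. What remains is that the protocol describes no enquiry for completers, and what is asked at a visit is protocol content.

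A reader might also infer that the whole safety report would be empty, that incidence is shown to be biased low, or that the study would wrongly support the safety of its procedures. None of these is supported:

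- Emptiness applies only to the literal incidence table. The listings and the summary of events leading to discontinuation do not depend on that term.
- Under-recording is a possibility limited mainly to delayed events, and no figure establishes it.
- No objective in section 5 concerns safety, section 7.1.4 says the study is not meant to validate the device's safety, and no conclusion about the walk test is planned from event incidence.

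**Conclusion.** The point holds in two limited parts. The conflict within section 9 is certain: it rests only on the text and on the absence of any study treatment in sections 7.1.1 to 7.1.3. The possible under-recording of delayed soreness, myalgia and fatigue in completers is a risk, conditional on staff following the visit lists as written and on the case report form adding nothing. Its size cannot be estimated from the documents.

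Neither part touches a study objective. This is a low-priority correction, worth making because it is nearly free. The inconsistent enrolment totals (50 patients plus 20 controls in sections 7.1 and 10.2; 70 plus 20 in section 7.3) would also affect the denominator of any percentage, but that is a separate matter.

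**What to change.** - **Section 9:** define the tabulated events as those occurring from consent to last contact, and replace relationship to treatment by relationship to study procedures in both the table rule and the causality scale. The four levels can stay. Tables and listings then share one basis, and the period also covers the post-withdrawal contact in section 7.2.2.
- **Section 7.1.3:** add one adverse-event question at Visit 2 for every participant, patient or healthy volunteer, covering the time since Visit 1. Adjust the sentence in section 7.1 that limits Visit 2 to device measurements. If the case report form already has such a question, it is enough to say so here.

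The blinding in section 7.1 should be kept in mind when deciding who asks: the device assessor is blinded to diagnosis, medical history and clinical test results, so another team member could ask, or the question could follow the measurement.

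The cost is a few reworded sentences and about one minute at a visit that is already planned to take about 30 minutes.

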10 STATISTICAL METHODS AND PLANNED ANALYSES

10.1 General Considerations

All patients who participate in this study will be included in the analysis. Data collected in this study will be reported using summary tables, figures and patient data listings. Summary statistics (n, mean, median, standard deviation, minimum and maximum) will be calculated for the continuous variables and shift tables and/or frequencies, and percentages will be produced for the categorical variables. Due to the exploratory nature of this study, no formal inferential statistical tests will be performed.

10.2 Determination of Sample Size

50 patients and 20 healthy subjects will be enrolled in this study. No formal sample size calculations have been performed. This is an exploratory pilot-study and is not powered to make any statistical inferences.

10.3 Demographics and Baseline Characteristics

Demographic and baseline data on medical history and neuromuscular disease history as well as patient-related data will be summarized using exploratory and descriptive statistics for continuous variables and frequency distribution for categorical variables. To compare the mean values of two groups, the t-test will be used, to compare frequencies between two groups, the chi-square test. Correlations are calculated by using the Spearman and Pearson coefficient.

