5.2 Secondary Objectives

The secondary objectives of this study are

- to provide reference values for stiffness, muscle tone, relaxation periods and elasticity of various muscles in patients with dystrophic or non-dystrophic myotonia,
- to provide reference values for stiffness, muscle tone, relaxation periods and elasticity of various muscles in patients with non-myotonic neuromuscular disorders,
- assess correlations between to compare result values for stiffness, muscle tone, relaxation periods and elasticity with clinical muscle function tests, measured by clinical evaluation (MRC-scale) and the 6-minute walk test,
- assess correlations between subcutaneous fat and muscle thickness and echogenicity, measured by muscle ultrasound and result values for stiffness, muscle tone, relaxation periods and elasticity

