6.3 Number of patients

Approximately 70 patients will be enrolled, about 3-5 each in the following disease groups: Limb-Girdle-Muscular Dystrophy (LGMD), Myotonic Dystrophies Type 1 and 2 (DM1, DM2), Late-Onset-Pompe Disease (LOPD), Distal Myopathies, Congenital Myotonia, Spinal muscular atrophy Type 3 (SMA3), Amyotrophic lateral sclerosis (ALS) and peripheral Polyneuropathies (CIDP, HMSN). 20 healthy age- and gender-matched patients will be enrolled as a control group.

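### Simple Spearman and Pearson coefficients across ten diagnoses of 3-5 patients mix between-disease differences with any within-disease relation; report a disease-adjusted coefficient beside them

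*Protocol*

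**What the plan says.** The third and fourth secondary objectives in protocol section 5.2 are correlations. The third sets the device values (stiffness, tone, relaxation, elasticity) against strength and walking: "with clinical muscle function tests, measured by clinical evaluation (MRC-scale) and the 6-minute walk test". The fourth is to "assess correlations between subcutaneous fat and muscle thickness and echogenicity, measured by muscle ultrasound and result values for stiffness" and the other device parameters.

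The method is one sentence in section 10.3: "Correlations are calculated by using the Spearman and Pearson coefficient". It mentions no adjustment, stratification or unit of analysis, and it does not say which coefficient goes with which scale.

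Section 6.3 plans "about 3-5 each in the following disease groups" and lists LGMD, DM1, DM2, LOPD, distal myopathies, congenital myotonia, SMA3, ALS, CIDP and HMSN. Sections 7.1 and 10.2 give 50 patients and 20 healthy volunteers. MRC grades, ultrasound and device readings are all taken at the same sites: "on both sides thenar and hypothenar, m. biceps brachii, m. triceps brachii, m. deltoideus, m. quadriceps femoris, m. tibialis anterior and gastrocnemius muscles".

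**The concern.** The protocol itself expects the diagnoses to differ in the variables being correlated. Section 4 presents stiffness and delayed relaxation as hallmarks of the myotonic disorders, selective fatty infiltration and atrophy as features of several limb-girdle dystrophies, and atrophy without fatty change as the pattern in motor neuron disease and neuropathy. Section 7.1.6 gives dystrophies and neurogenic disorders different ultrasound patterns. Diagnosis can therefore move both variables in a pair.

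A simple coefficient across diagnoses cannot tell two situations apart. In one, stiffer muscle goes with weaker or more echogenic muscle among patients with the same disease. In the other, diseases with stiff muscle merely happen to be diseases with a certain strength or ultrasound picture. Only the first supports the device as a marker of muscle state within a disease. Section 8.2 hopes to measure treatment effects with it, which is a question about patients who share a diagnosis. Opposite between- and within-disease relations could also cancel, so a real relation might be missed.

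**Working it through.** The protocol gives no correlation, variance or precision figure to reproduce, so the check is structural, with assumed variance components shown as ranges.

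**Inputs from the protocol**
- Diagnoses: 10 (section 6.3, counting DM1/DM2 and CIDP/HMSN separately).
- Patients per diagnosis: 3-5 (section 6.3). 10 x 5 = 50, the total in section 10.2; 10 x 3 = 30.
- Scales: MRC 0-5 and Heckmatt I-IV are ordinal; device values, thicknesses and 6MWT distance are continuous (section 7.1.2).

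**Inputs assumed**
- Share of variance due to disease, f, equal for both variables: 0.2, 0.3, 0.5, 0.7.
- Correlation of disease means, rho_b: 0, 0.8, 1.0.
- Correlation within disease, rho_w: 0.

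**Step 1: can each disease be analysed alone?** The Fisher interval is tanh(atanh(r) ± 1.96/√(n - 3)). For r = 0.3, atanh(r) = 0.310.
- n = 5: 0.310 ± 1.386, giving -0.79 to 0.93.
- n = 3: n - 3 = 0, so no interval exists.
- n = 50: the interval is 0.02 to 0.53.

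Section 6.3 speaks of about 70 patients, where section 10.2 has 50. Seven per disease (70/10) would give 0.310 ± 0.98, or -0.59 to 0.86, which does not change the conclusion.

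**Step 2: what does a coefficient across diseases estimate?** With disease share f in both variables, approximately r_pooled = f·rho_b + (1 - f)·rho_w. With rho_w = 0 and rho_b = 0.8 this is 0.16, 0.24, 0.40 and 0.56 for the four values of f. With only ten disease means the average is a little lower. Simulation (2000 data sets per setting, 10 diseases x 5 patients, one value per patient) gave:

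| f | rho_b = 0 | rho_b = 0.8, Pearson | rho_b = 0.8, Spearman | rho_b = 1.0, Pearson |
|---|---|---|---|---|
| 0.2 | 0.00 | 0.14 | 0.14 | 0.18 |
| 0.3 | 0.00 | 0.22 | 0.21 | 0.27 |
| 0.5 | 0.00 | 0.36 | 0.35 | 0.45 |
| 0.7 | 0.00 | 0.51 | 0.49 | 0.65 |

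Centring both variables on their disease means returned an average of about 0.00 in every setting. Because each patient contributes one value, the result does not depend on how the muscle sites are handled.

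**Step 3: what does adjustment cost?** Ten groups need nine indicator terms.
- 50 patients: residual degrees of freedom fall from 48 to 39, and √(48/39) = 1.11.
- 30 patients: they fall from 28 to 19, and √(28/19) = 1.21.

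**The case against.** The strongest reply is that section 10.3 only names two coefficients. Unit of analysis, strata and adjustment often go into an SAP, and an adjusted Spearman coefficient would not conflict with the sentence. That is fair as to missing detail. The point here is narrower: the method as stated suits this design poorly, and a better one is available from data already collected.

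A second reply is that the objectives never ask for a within-disease relation. Whether device values track strength or echogenicity across neuromuscular disease is a legitimate descriptive question. This stands, and it is why both coefficients should be shown rather than one replacing the other. Grouping by myotonic and non-myotonic disorders, as the objectives do, would help, but each of those groups still contains several diagnoses.

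A third is that the sizes rest on assumptions. This also stands. Section 4 stresses variability within a single disease, and section 7.1.6 reports raised muscle echo in several disease types. A low disease share is therefore plausible, and at 0.2 the pooled value is only about 0.14.

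Three stronger readings are tempting but unsupported.
- **Sixteen sites as independent rows.** Eight muscles on two sides give 50 x 16 = 800 patient-site rows. With an assumed within-person correlation of 0.5 in both variables, the design effect would be 1 + 15 x 0.25 = 4.75 and the effective size about 168. The protocol does not say that sites will be pooled, and a per-muscle analysis avoids the problem.
- **Controls inflating the coefficient.** Section 7.1 says "Both patients and healthy volunteers will perform the following assessments", which concerns assessments. Nothing says that controls enter the correlations.
- **Misleading p-values or intervals.** None is planned for the correlations. Section 10.1 disclaims formal tests, the t-test and chi-square test in 10.3 are for comparing two groups, and the intervals in 10.5 are for change between visits.

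**Conclusion.** The point holds in limited form. Two secondary objectives rest on simple coefficients, single-disease estimates are nearly uninformative at 3-5 patients, and a coefficient across diseases can be clearly non-zero when nothing is going on within any disease. The average is about 0.14-0.51 for disease variance shares of 0.2-0.7 with disease means correlated 0.8. It is zero if the disease means are uncorrelated. These variance shares and correlations are assumptions; the protocol gives none.

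The exploratory label does not settle the matter, because the issue is what the coefficient means rather than whether it is tested. The primary objective and the reference-value objectives are not affected. The change is worth making, but it is a moderate point.

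**What to change.** Amend section 10.3 to state the following.
- Correlations for the third and fourth secondary objectives are computed in patients, separately for each muscle, with one value per patient (mean of left and right).
- Report a Spearman partial correlation adjusted for disease group beside the unadjusted coefficient. Where a disease has very few patients, use merged groups defined in advance.
- Interpret the unadjusted coefficient as association across diseases only.
- Any interval for the adjusted coefficient uses the reduced degrees of freedom.
- Use Pearson only for pairs of continuous variables, and Spearman wherever MRC or Heckmatt grades are involved.

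The cost is a little more analysis and about nine degrees of freedom: intervals about 11% wider with 50 patients, and about 20% wider if each disease has only three. Merging groups recovers some of this but leaves some mixing of diagnoses within the merged groups. No new data are needed.
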